7.6.2.2 Serious Adverse Events

All reported serious adverse events (SAEs) will be listed by System Organ Class (SOCs) and Preferred Terms (PTs) for all enrolled subjects. SAEs with onset time from the start of study treatment, up to and including 32 days after the start of study treatment will be included in the summary tables. SAEs will be coded and grouped into PT by SOC (see [section 7.6.2.3](#)).

7.6.2.3 Adverse Events

All AEs will be coded and grouped into PT by SOC, using current version of Medical Dictionary for Regulatory Activities (MedDRA). All AEs will be summarized and listed by SOCs and PTs.

Non-serious AEs with onset time from the start of study treatment, up to and including 120 hours after the start of study treatment will be included in the summary tables. Events will be assigned to the study treatment administered to the subject. The proportion of subjects having an adverse event will be calculated as the number of subjects experiencing the event, divided by the total number of subjects receiving study treatment.

All AE listings will indicate the unique subject identifier, age, gender, current treatment, the date and time of onset, the date and time of resolution, day of onset relative to the start of treatment, action taken, investigator's assessment of severity and relationship to study drug. Additional listings will be provided for adverse events leading to discontinuation and adverse events without recorded resolution. Summaries of adverse events will include adverse events, adverse events by intensity and adverse events by relationship.

Where a subject has the same adverse event, based on preferred terminology, reported multiple times in a single analysis period, the subject will only be counted once at the preferred terminology level in adverse event frequency tables.

Where a subject has multiple adverse events within the same system organ class in a single analysis period, the subject will only be counted once at the system organ class level in adverse event frequency tables.

When a subject has the same adverse event, based on preferred terminology, reported multiple times in a single analysis period, the following criteria, in order of precedence, will be used to select the event to be included in summary tables:

- Relationship to study medication
- Intensity of event
- Onset date and time

When reporting adverse events by intensity, in addition to providing a summary table based on the event selection criteria detailed above, summary tables will also be provided based on the most intense event during the analysis period - independent of relationship to study medication. For these tables, the following criteria, in order of precedence, will be used to select the event to be included in summary tables:

- Intensity of event
- Onset date and time

Subjects will only be counted once in the 'Total' at their maximum intensity, regardless of SOC or PT.

7.6.2.4 Clinical Laboratory Evaluations

The results of all protocol-specified clinical laboratory tests will be listed. Scheduled laboratory measurements and corresponding change from baseline values will be summarized by treatment and scheduled time points for each laboratory test.

The criteria used for classifying laboratory test results as markedly abnormal will be listed.

Laboratory results for subjects with any marked laboratory abnormality (scheduled and unscheduled) will be listed. This listing will include all observations for the specific laboratory test and subject, not only the marked laboratory abnormalities. The frequency of subjects with any marked laboratory abnormality as well as hematology, serum chemistry, and urinalysis marked abnormalities, based on pre-specified criteria (see Table 7.6.2.4-1), will be presented.

Troponin T will be summarized descriptively by treatment for each time point, as well as change from baseline. Geometric mean and coefficient of variation (%CV) will also be presented for the original values and percent of baseline.

Table 7.6.2.4-1: Laboratory MA Criteria

Parameter	Test Code	Direction of Change	MA Criteria in US Standard Units (apply to labs collected after baseline only)	MA Criteria in SI Units (apply to labs collected after baseline only)
HEMATOLOGY				
Hemoglobin	HB	Low only	> 2 g/dl decrease compared to pre-dose or Value ≤ 8 g/dl	> 20 g/l decrease compared to pre-dose or Value ≤ 80 g/l
Hematocrit	HCT	Low only	< 0.75 × pre-dose	< 0.75 × pre-dose
Erythrocytes	RBC	Low only	< 0.75 × pre-dose	< 0.75 × pre-dose
Platelet Count	PLAT	Low Only	< 100,000/mm ³ (or < 100× 10 ⁹ cells/L)	< 100× 10 ⁹ cells/L
Leukocytes	WBC	Low/High	< 0.75 × LLN or > 1.25 × ULN, or if pre-dose < LLN then use < 0.8 × pre-dose or > ULN if pre-dose > ULN then use > 1.2 × pre-dose or < LLN	< 0.75 × LLN or > 1.25 × ULN, or if pre-dose < LLN then use < 0.8 × pre-dose or > ULN if pre-dose > ULN then use > 1.2 × pre-dose or < LLN
Neutrophils (absolute)	NEUTA	Low Only	< 1.0 × 10 ³ cells/μL	< 1.0 × 10 ⁹ cells/L
LIVER/KIDNEY				
Alkaline Phosphatase	ALP	High only	> 2 × ULN	> 2 × ULN
Aspartate Aminotransferase	AST	High only	> 3 × ULN, > 5 × ULN, > 10 × ULN	> 3 × ULN, > 5 × ULN, > 10 × ULN
Alanine Aminotransferase	ALT	High only	> 3 × ULN, > 5 × ULN, > 10 × ULN	> 3 × ULN, > 5 × ULN, > 10 × ULN
Bilirubin, Total	TBILI	High only	> 2 × ULN	> 2 × ULN

Table 7.6.2.4-1: Laboratory MA Criteria

Parameter	Test Code	Direction of Change	MA Criteria in US Standard Units (apply to labs collected after baseline only)	MA Criteria in SI Units (apply to labs collected after baseline only)
Blood Urea Nitrogen	BUN	High only	$>2 \times \text{ULN}$	$>2 \times \text{ULN}$
ELECTROLYTES				
Sodium, Serum	NA	Low/High	$< 0.95 \times \text{LLN}$ or $> 1.05 \times \text{ULN}$, or if pre-dose $< \text{LLN}$ then use $< 0.95 \times \text{pre-dose}$ or $> \text{ULN}$ if pre-dose $> \text{ULN}$ then use $> 1.05 \times \text{pre-dose}$ or $< \text{LLN}$	$< 0.95 \times \text{LLN}$ or $> 1.05 \times \text{ULN}$, or if pre-dose $< \text{LLN}$ then use $< 0.95 \times \text{pre-dose}$ or $> \text{ULN}$ if pre-dose $> \text{ULN}$ then use $> 1.05 \times \text{pre-dose}$ or $< \text{LLN}$
Potassium, Serum	K	Low/High	$< 0.9 \times \text{LLN}$ or $> 1.1 \times \text{ULN}$, or if pre-dose $< \text{LLN}$ then use $< 0.9 \times \text{pre-dose}$ or $> \text{ULN}$ if pre-dose $> \text{ULN}$ then use $> 1.1 \times \text{pre-dose}$ or $< \text{LLN}$	$< 0.9 \times \text{LLN}$ or $> 1.1 \times \text{ULN}$, or if pre-dose $< \text{LLN}$ then use $< 0.9 \times \text{pre-dose}$ or $> \text{ULN}$ if pre-dose $> \text{ULN}$ then use $> 1.1 \times \text{pre-dose}$ or $< \text{LLN}$
Chloride, Serum	CL	Low/High	$< 0.9 \times \text{LLN}$ OR $> 1.1 \times \text{ULN}$, or if pre-dose $< \text{LLN}$ then use $< 0.9 \times \text{pre-dose}$ or $> \text{ULN}$ if pre-dose $> \text{ULN}$ then use $> 1.1 \times \text{pre-dose}$ or $< \text{LLN}$	$< 0.9 \times \text{LLN}$ OR $> 1.1 \times \text{ULN}$, or if pre-dose $< \text{LLN}$ then use $< 0.9 \times \text{pre-dose}$ or $> \text{ULN}$ if pre-dose $> \text{ULN}$ then use $> 1.1 \times \text{pre-dose}$ or $< \text{LLN}$
Calcium, Total	CA	Low/High	$< 0.8 \times \text{LLN}$ or $> 1.2 \times \text{ULN}$, or if pre-dose $< \text{LLN}$ then use $< 0.75 \times \text{pre-dose}$ or $> \text{ULN}$ if pre-dose $> \text{ULN}$ then use $> 1.25 \times \text{pre-dose}$ or $< \text{LLN}$	$< 0.8 \times \text{LLN}$ or $> 1.2 \times \text{ULN}$, or if pre-dose $< \text{LLN}$ then use $< 0.75 \times \text{pre-dose}$ or $> \text{ULN}$ if pre-dose $> \text{ULN}$ then use $> 1.25 \times \text{pre-dose}$ or $< \text{LLN}$
Bicarbonate	HCO3	Low/High	$< 0.75 \times \text{LLN}$ or $> 1.25 \times \text{ULN}$, or if pre-dose $< \text{LLN}$ then use $< 0.75 \times \text{pre-dose}$ or $> \text{ULN}$ if pre-dose $> \text{ULN}$ then use $> 1.25 \times \text{pre-dose}$ or $< \text{LLN}$	$< 0.75 \times \text{LLN}$ or $> 1.25 \times \text{ULN}$, or if pre-dose $< \text{LLN}$ then use $< 0.75 \times \text{pre-dose}$ or $> \text{ULN}$ if pre-dose $> \text{ULN}$ then use $> 1.25 \times \text{pre-dose}$ or $< \text{LLN}$
OTHER CHEMISTRY				
Creatine Kinase	CK	High only	$> 5 \times \text{ULN}$	$> 5 \times \text{ULN}$
Total Protein	TPRO	Low/High	$< 0.9 \times \text{LLN}$ or $> 1.1 \times \text{ULN}$, or if pre-dose $< \text{LLN}$ then use $0.9 \times \text{pre-dose}$ or $> \text{ULN}$ if pre-dose $> \text{ULN}$ then use $1.1 \times \text{pre-dose}$ or $< \text{LLN}$	$< 0.9 \times \text{LLN}$ or $> 1.1 \times \text{ULN}$, or if pre-dose $< \text{LLN}$ then use $0.9 \times \text{pre-dose}$ or $> \text{ULN}$ if pre-dose $> \text{ULN}$ then use $1.1 \times \text{pre-dose}$ or $< \text{LLN}$

Table 7.6.2.4-1: Laboratory MA Criteria

Parameter	Test Code	Direction of Change	MA Criteria in US Standard Units (apply to labs collected after baseline only)	MA Criteria in SI Units (apply to labs collected after baseline only)
Glucose, Fasting Serum	GLUCF	Low/High	< 0.8 × LLN or > 1.5 × ULN, or if pre-dose < LLN then use < 0.8 × pre-dose or > ULN if pre-dose > ULN then use > 2.0 × pre-dose or <LLN	< 0.8 × LLN or > 1.5 × ULN, or if pre-dose < LLN then use < 0.8 × pre-dose or > ULN if pre-dose > ULN then use > 2.0 × pre-dose or <LLN
Uric Acid	URIC	High only	> 1.5 × ULN, or if pre-dose > ULN then use > 2 × pre-dose	> 1.5 × ULN, or if pre-dose > ULN then use > 2 × pre-dose
Albumin		Low only	≤ 2 g/dL	≤ 20 g/L
URINALYSIS				
Protein, Urine	UPRO	High only	If missing pre-dose then use ≥ 2, or if value ≥ 4, or if pre-dose = 0 or 0.5 then use ≥ 2, or if pre-dose = 1 then use ≥ 3, or if pre-dose = 2 or 3 then use ≥ 4	If missing pre-dose then use ≥ 2, or if value ≥ 4, or if pre-dose = 0 or 0.5 then use ≥ 2, or if pre-dose = 1 then use ≥ 3, or if pre-dose = 2 or 3 then use ≥ 4
Blood, Urine	UBLD	High only	If missing pre-dose then use ≥ 2, or if value ≥ 4, or if pre-dose = 0 or 0.5 then use ≥ 2, or if pre-dose = 1 then use ≥ 3, or if pre-dose = 2 or 3 then use ≥ 4	If missing pre-dose then use ≥ 2, or if value ≥ 4, or if pre-dose = 0 or 0.5 then use ≥ 2, or if pre-dose = 1 then use ≥ 3, or if pre-dose = 2 or 3 then use ≥ 4
Leukocyte Esterase, Urine	ULEUK	High only	If missing pre-dose then use ≥ 2, or if value ≥ 4, or if pre-dose = 0 or 0.5 then use ≥ 2, or if pre-dose = 1 then use ≥ 3, or if pre-dose = 2 or 3 then use ≥ 4	If missing pre-dose then use ≥ 2, or if value ≥ 4, or if pre-dose = 0 or 0.5 then use ≥ 2, or if pre-dose = 1 then use ≥ 3, or if pre-dose = 2 or 3 then use ≥ 4
RBC, Urine	URBC	High only	If missing pre-dose then use ≥ 2, or if value ≥ 4, or if pre-dose = 0 or 0.5 then use ≥ 2, or if pre-dose = 1 then use ≥ 3, or if pre-dose = 2 or 3 then use ≥ 4	If missing pre-dose then use ≥ 2, or if value ≥ 4, or if pre-dose = 0 or 0.5 then use ≥ 2, or if pre-dose = 1 then use ≥ 3, or if pre-dose = 2 or 3 then use ≥ 4
WBC, Urine	UWBC	High only	If missing pre-dose then use ≥ 2, or if value ≥ 4, or	If missing pre-dose then use ≥ 2, or if value ≥ 4, or

Table 7.6.2.4-1: Laboratory MA Criteria

Parameter	Test Code	Direction of Change	MA Criteria in US Standard Units (apply to labs collected after baseline only)	MA Criteria in SI Units (apply to labs collected after baseline only)
			if pre-dose = 0 or 0.5 then use ≥ 2 , or if pre-dose = 1 then use ≥ 3 , or if pre-dose = 2 or 3 then use ≥ 4	if pre-dose = 0 or 0.5 then use ≥ 2 , or if pre-dose = 1 then use ≥ 3 , or if pre-dose = 2 or 3 then use ≥ 4

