6.6 Potential Drug Induced Liver Injury (DILI)

Wherever possible, timely confirmation of initial liver-related laboratory abnormalities should occur prior to the reporting of a potential DILI event. All occurrences of potential DILIs, meeting the defined criteria, must be reported as SAEs (see [Section 6.1.1](#) for reporting details).

Potential drug induced liver injury is defined as:

Aminotransaminases (ALT or AST) elevation > 3 times upper limit of normal (ULN) if baseline values are within the normal range, or > 2 times the baseline values in case of baseline values above the upper limit of normal (ULN) AND Total bilirubin > 2 times ULN, without initial findings of cholestasis (elevated serum alkaline phosphatase)

AND No other immediately apparent possible causes of aminotransaminases (AT) elevation and hyperbilirubinemia, including, but not limited to, worsening heart failure, viral hepatitis, pre-existing chronic or acute liver disease, or the administration of other drug(s), herbal medications or substances known to be hepatotoxic

Given the short treatment course, baseline liver enzyme testing will be performed at Pre-randomization and post-treatment liver enzyme testing will be performed at Hour 120 and Day 32.

All occurrences of potential DILIs, meeting the defined criteria, must be reported as SAEs (see [Section 6.1.1](#) for reporting details).

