8.5 Interim Analyses

Two interim analyses will be performed for this study. An interim analysis will be performed following the completion of the last visit at Hour 120 in Part I (Cohort 1). The analysis will include data for all Cohort 1 subjects through at least Hour 120. The DMC, Executive Committee and representatives from the Sponsor will assess hypotension, as well as additional safety information, in addition to any available endpoint events. The outcome will determine whether 12 µg/kg/min is a sufficiently tolerated dose to be used in Part II (Cohort 2). The dose selection decision for Part II will be made by the Sponsor in collaboration with the Executive Committee, with input from the DMC. The doses for Part II (Cohort 2) will be determined based on general guiding principles and considered in the context of the totality of the data. For example, some of the critical information that will be considered evaluating the suitability 12 µg/kg/min for Part II will include the percentage of subjects completing the 48 hour infusion, percentage of subjects with temporary interruptions or permanent discontinuation of study drug, percentage of subjects with clinically relevant hypotension, percentage of subjects with symptomatic hypotension, and other key safety endpoints of interest (eg, renal function).

The second interim analysis will be performed when 210 randomized subjects reach the last visit at Day 32 in Part II (Cohort 2) in order to facilitate drug development decisions. The study analysis team will then provide top-line results to the project team.

After each DMC review, the Sponsor will be advised by the DMC Chair as to whether the study is safe to proceed as written, that the study should be modified, or that the study should be stopped. In addition to these periodic reviews, the DMC will review the unblinded data from Part I in parallel with the review by the executive committee and the Sponsor. A similar recommendation will be provided to the Sponsor, that the study is to proceed as written, or should be modified or stopped.

Analyses will consist of summaries of the available data. No formal inferences requiring any adjustment to statistical significance level will be performed

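### The AST, ALT, ALP, bilirubin and BUN marked-abnormality limits ignore the pre-dose value, so subjects already abnormal at entry inflate the counts in every arm and dilute the active-to-placebo ratio

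*SAP*

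**What the plan says.** SAP Table 7.6.2.4-1 sets the marked-abnormality criteria. In its liver/kidney block, AST and ALT are flagged at "> 3 × ULN, > 5 × ULN, > 10 × ULN", and ALP, total bilirubin and BUN at more than 2 × ULN. None of the five rows mentions the pre-dose value. The column headings say that the criteria "apply to labs collected after baseline only", which restricts the samples, not the subjects.

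Other rows of the table do use the pre-dose value. Uric acid, for example, is flagged at "> 1.5 × ULN, or if pre-dose > ULN then use > 2 × pre-dose". WBC, sodium, potassium, chloride, calcium, bicarbonate, total protein and glucose have the same kind of branch. Hematocrit and erythrocytes are compared with pre-dose, as is hemoglobin in part, and the urinalysis grades depend on it.

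SAP 8.4 says that incidence tabulations of marked abnormalities, with ALT above 3 × ULN as its example, use the worst measurement in the visit window. Protocol 8.3.4 and SAP 4.2.2 name the incidence of marked laboratory abnormalities as a safety endpoint.

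The glucose row is headed "Glucose, Fasting Serum" (test code GLUCF). Protocol 5.3.5.2 lists glucose with no fasting condition.

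**The concern.** The trial enrolls patients with acute decompensated heart failure, and some may arrive with raised liver or urea values. Protocol 6.6 itself lists worsening heart failure among the other causes of raised aminotransferases and bilirubin. Protocol 3.3 sets no entry limit on AST, ALT, ALP or BUN, excludes bilirubin only above 3 mg/dL and excludes eGFR only below 30. A subject can therefore exceed a limit before the infusion starts.

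Under the table as written, such a subject becomes a post-baseline marked abnormality at the first later sample still above the limit. A fall in ALT from 6 to 3.5 × ULN is counted just like a rise from normal to 3.5 × ULN. SAP 7.1 plans no significance testing, so readers will compare doses from these counts directly, in arms of about 70 subjects in Part II. If many of the counted subjects were abnormal on arrival, a real liver or renal signal looks smaller in relative terms.

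**Working it through.** The plan states no figure on this point, so there is none to reproduce. The check has three steps.

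**1. Can an eligible subject exceed a limit before dosing?**

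- AST, ALT, ALP, BUN: yes, because Protocol 3.3 sets no cap.
- Bilirubin: the flag is 2 × ULN. The documents give no ULN. With an assumed ULN of 1.0 to 1.3 mg/dL the flag lies at 2 × 1.0 = 2.0 to 2 × 1.3 = 2.6 mg/dL, inside the range allowed up to 3 mg/dL. (For Germany the liver criterion refers to an appendix that is not in the text supplied.)

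**2. What does prevalence at entry do to the table?**

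Let f be the share of each arm already over the limit who are still over it at a post-baseline sample, and p the new-onset rate among the rest. The tabulated rate is

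q = f + (1 − f) × p.

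The tabulated risk difference is (1 − f) × (p_active − p_placebo). None of these values is in the documents. I assume p = 5% on placebo and 10% on active, and vary f:

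| f | Placebo | Active | Ratio | Risk difference (points) |
|---|---|---|---|---|
| 0% | 5.0% | 10.0% | 2.00 | 5.0 |
| 2% | 6.9% | 11.8% | 1.71 | 4.9 |
| 5% | 9.75% | 14.5% | 1.49 | 4.75 |
| 10% | 14.5% | 19.0% | 1.31 | 4.5 |
| 20% | 24.0% | 28.0% | 1.17 | 4.0 |

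Example at f = 10%: placebo 0.10 + 0.90 × 0.05 = 0.145; active 0.10 + 0.90 × 0.10 = 0.190; ratio 0.190 / 0.145 = 1.31.

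A second set, with p = 3% and 9%, behaves in the same way: the ratio falls from 3.00 to 2.19, 1.73 and 1.43 at f = 2%, 5% and 10%, and the risk difference from 6.0 to 5.9, 5.7 and 5.4 points.

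If the drug has no effect, p is equal in the arms. With f balanced by randomization, q is then equal too: ratio 1, difference 0, whatever f is.

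**3. What does counting new crossings restore?**

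With all treated subjects as denominator, the rate becomes (1 − f) × p. At f = 10% this is 0.90 × 0.05 = 4.5% against 0.90 × 0.10 = 9.0%: ratio 2.0, difference 4.5 points. With only subjects below the limit at pre-dose as denominator, it is 5% against 10%. The correction therefore restores the ratio. The difference per treated subject is 4.5 points either way.

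**The case against.** The strongest reply is that baseline is handled elsewhere. SAP 7.6.2.4 summarizes change from baseline by treatment and time point for every test, and lists every observation of that test for each flagged subject, so a high pre-dose value is visible. The comparison is with randomized placebo, the analysis is descriptive, and the prevalences above are assumptions. Platelets, neutrophils, CK and albumin also have fixed limits, so the contrast within the table is not as clean as the five rows suggest.

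Much of this stands. Randomization rules out a systematic false difference, and the size of the dilution cannot be fixed from the documents. But mean changes can hide a few subjects with large rises, and a listing leaves the reader to do the sorting. No planned output shown gives, by arm, the number of subjects who newly reached a liver or BUN limit.

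Two stronger readings are tempting, and the documents do not support them.

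- *The table contradicts Protocol 6.6.* That section's aminotransferase limb does depend on baseline: "elevation > 3 times upper limit of normal (ULN) if baseline values are within the normal range", otherwise more than twice baseline. The two thresholds meet at a baseline of 1.5 × ULN (2 × 1.5 = 3) and differ elsewhere above ULN. From 2 × ULN, a rise to 3.5 is counted by the SAP but is below that limb (4). From 1.2 × ULN, a rise to 2.6 passes that limb (2.4) but not the SAP limit. However, Protocol 6.6 is a composite that also requires bilirubin above 2 × ULN without initial cholestasis and no other apparent cause, and it serves SAE reporting. Passing one limb does not meet the rule. A single-analyte count can coexist with it.
- *A creatinine rise cannot be flagged.* The table shows no creatinine row, and Protocol 8.5 names renal function as an input to dose selection. But creatinine receives change-from-baseline summaries, and SAP 7.7.2 analyzes worsening renal function in the same manner as the primary endpoint. Its threshold is not visible and may lie in redacted text.

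**Conclusion.** The point holds for five rows: AST, ALT, ALP, total bilirubin and BUN. As written, subjects over a limit at entry are counted as marked abnormalities in a named safety endpoint. Counts are inflated in every arm and the ratio of active to placebo is diluted, from 2.0 to 1.31 or 1.17 at prevalences of 10% or 20%. The absolute difference is only slightly reduced. These figures rest on assumed onset rates, assumed prevalence equal in the arms, and the assumption that the counted subjects stay over the limit. At 2% prevalence the ratio is still 1.71.

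A reader might infer that the table would manufacture a drug effect. It would not: in expectation the null comparison is unaffected, although chance imbalance at baseline remains possible.

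The glucose row is a separate and smaller matter. No fasting sample is scheduled, and Protocol 5.3.5.2 lists only glucose, so the label does not match the data. It should not be read as ignoring baseline, because the row already has pre-dose branches. Nor do the documents show how the label would be programmed.

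**What to change.** - For the five rows, count a subject only when the limit is newly crossed relative to pre-dose, with pre-dose defined as in SAP 8.2. For AST and ALT, a subject already in one class counts only on reaching the next higher class. Alternatively, add a baseline-to-worst shift table by arm.
- Keep the fixed-ULN counts as a secondary display. They still show subjects who start above the top limit and cannot newly cross it.
- State the denominator, and how a missing pre-dose value is treated. The urinalysis protein, blood, leukocyte esterase and cell rows already have such a rule.
- Change the glucose row from fasting serum (GLUCF) to the glucose actually collected. Its pre-dose branches can stay.
- Add a cross-reference from the table to the worsening-renal-function analysis in SAP 7.7.2. No new creatinine threshold is needed.

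The cost is a table edit, some programming and one more table. All the data are already collected.

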7.6.2.5 ECG

All recorded ECGs (heart rate (HR), QT (QT, Bazett’s corrected QT [QTcB], Fridericia's corrected QT [QTcF]), PR and QRS intervals) will be listed.

Summaries of ECG parameters (heart rate (HR), QT (QT, QTcF), PR and QRS intervals) will be tabulated by time point and treatment. Summaries of ECG parameters will include change from baseline at list of time points.

If QTcF is not available in the database, QTcF will be calculated using the reported uncorrected QT Interval and Heart Rate, and the following formula:

$$QTcF = \frac{QT}{(60/HEART\ RATE)^{1/3}}$$

Subjects with ECG intervals outside of a pre-specified range will also be listed.

The following criteria will be used to determine ECG results that are outside of a pre-specified range:

PR (msec):	Value > 200
QRS (msec):	Value > 120
QT (msec):	Value > 500 or change from baseline > 30
QTcF (msec):	Value > 450 or change from baseline > 30

